### 3.5 Sample Size

Table 1 provides the required sample size per treatment group when the number of migraine days per 28-day period is used as the primary outcome measure. Sample size calculations are based on the clinically meaningful difference between active and sham treatment groups in change from baseline. Assuming a type I error of 5% (two-sided) and 90% power, Table 1 displays the required sample sizes for different values of the common standard deviation (2.0, 2.5, 3.0 and 3.5) and the presumed difference between treatment groups (1, 1.5 and 2 days). Selecting an improvement of 1 day and a common standard deviation of 2.5 requires 133 subjects per treatment group. With 15% drop-out during the randomized treatment period, a total of 160 subjects per treatment group (or 320 subjects total) would need to be randomized.

**Table 1: Required Sample Size per Treatment Group  
Assuming Type I Error ( $\alpha$ ) = 5% (two-sided) and 90% Power**

Variability (Common SD*, $\sigma$ )	Clinically Significant Improvement: Active – Sham = $\Delta$		
	1-day	1.5-day	2-day
2.0	86	--	--
2.5	133	60	34
3.0	191	86	49
3.5	259	115	66

\*Estimated standard deviation for change from baseline. Standard deviations for baseline and post treatment scores are between 2.0 to 3.5.

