### 5.1 Intent-to-Treat (ITT) Population

The Intention to treat (ITT) population includes all randomized subjects with at least one verified treatment post-training during the 12 week randomized period. The ITT population will be analyzed using the subject's randomized treatment regardless of which treatment the subject actually received.

The ITT is considered the primary analysis dataset, and will be used for all primary and secondary efficacy analyses.

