### 5.2 Per Protocol (PP) Population

The per protocol (PP) population includes all ITT subjects who received the correct treatment with no major protocol deviations which could affect the assessment of efficacy. Major protocol deviations include, but are not limited to, the following:

- The subject did not reach visit 6
- Less than 67% compliance with treatment per month in the randomized period (refer to section 6.3).

The final criteria for the PP population, regarding which protocol deviations warrant exclusions, will be determined when all data on protocol deviations are available and before breaking the blind.

If the difference in sample size between the ITT and PP populations is more than 5%, then the primary efficacy analyses will be repeated in the PP population.

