## 7.4 Efficacy

### 7.4.1 Primary Endpoint

The primary endpoint is the change from run-in to the last four weeks (Month 3) of the randomized period in the number of migraine days.

The diary data will collect for each day an indicator (1=Yes, 0=No, or missing) of whether the subject experienced a migraine. One 24 hour period per migraine will be designated as a migraine day.

The visit level value for a given subject is then the sum of the daily diary day indicators of whether the subject experienced a migraine which gives the number of days with a migraine. Calculations are as follows:

$$\text{Run-in Value} = \sum_{i=-z-28}^{-z} \text{Day } i, \text{ where Day } i = 1 \text{ (had a migraine)}$$

where  $z$  represents the subject's last day with diary data during the run-in period.

In the event that a subject does not 28 diary days in the run-in period the following rules will be used to calculate the run-in value:

1. If the number of diary days in the run-in period is less than 21, the run-in value will not be calculated, and will be considered missing.
2. If number of diary days in the run-in period is greater than or equal to 21, but less than 28, the run-in value would be calculated as:

$$\text{Run-in Value} = \sum_{i=-z-x}^{-z} \text{Day } i, \text{ where Day } i = 1 \text{ (had a migraine)}$$

where  $z$  represents the subject's last day with diary data during the run-in period, and  $x$  is the number of days with diary data during the run-in period.

To ensure consistency of the run-in value for all subjects, the value will be adjusted to reflect an estimated number of days with migraine per 28 day interval. For example, if a subject records data for  $x$  days out of 28 days and have  $y$  days with migraine, then the adjusted number of days with migraine in 28 days is  $(28/x)*y$ , with a maximum value of 28.

$$\text{Month 3 Value} = \sum_{i=57}^{84} \text{Day } i, \text{ where Day } i = 1 \text{ (had a migraine)}$$

In the event that a subject does not have at least 84 study days in the DB period the following rules will be used to calculate the Month 3 value:

3. If the number of study days in the DB period is less than 70, the month 3 value will not be calculated, but rather imputed to the run-in value (and thus resulting in a  $\text{Change}_{\text{Run-in}}=0$ , implying no change between periods).

Month 3 Value =Run-in Value

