## **Appendix 1: Sensitivity Analyses: Multiple Imputation and Control-based Pattern Mixture Model**

Multiple imputation will be used to impute missing data. First, any non-monotone missing data patterns will be made monotone by imputing the intermittent missing data using the Monte Carlo Markov Chain (MCMC) approach. This imputation will be performed 100 times, resulting in a dataset with 100 copies of monotone data. If no non-monotone missing data patterns exist, this step is not necessary. Missing data will then be imputed using the monotone regression method. The following factors/covariates will be included in the model: treatment, center and number of migraines in the 4-week run-in period.

The data will be analyzed by t-test and ANCOVA, for each of the 100 imputations, and the results combined using standard multiple imputation methodology to obtain the appropriate estimates of variability.

The control-based pattern mixture model is a sensitivity analyses which addresses the possibility that the missing data is missing not at random (MNAR). The sham group will act as the control; and, the observed data from this group will be used to impute the missing data in both the sham and active groups.

The method is designed to impute data from monotone missing data patterns, thus the patterns of missing data are first examined and described. Any non-monotone missing data patterns will be made monotone first by imputing the intermittent missing data using the Monte Carlo Markov Chain (MCMC) approach. This imputation will be performed 100 times, resulting in a dataset with 100 copies of monotone data. If no non-monotone missing data patterns exist, this step is not necessary.

To implement the control-based pattern mixture model, the missing endpoint assessment for treatment and sham subjects is then imputed based on a linear regression model using observed data in the sham group, with the missing assessment as the dependent variable. The following factors/covariates will also be included in the model: treatment, center and number of migraines in the 4-week run-in period.

The data will be analyzed by t-test and ANCOVA, for each of the 100 imputations, and the results combined using standard multiple imputation methodology to obtain the appropriate estimates of variability.

An example of SAS code that may be used to implement the MCMC intermittent missing data imputation is:

```
proc mi data=indsn out=outmono n impute=100 seed=startseed ;

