  class trt center;
  var trt center base depvar;
  mcmc chain=multiple impute=monotone;
run;
```

An example of SAS code that may be used to implement the control-based PMM is:

```
proc mi data=missdsn out=outdsn n impute=100 seed=startseed2 ;
```

```
class trt center;
var center base depvar;
monotone reg(/details);
mnar model(depvar / modelobs=(trt="sham"));
run;
```

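### The checks on the zero-change rule for early leavers do not use those subjects' own Month 1 and Month 2 diary counts, and section 3.5 does not say how its power allows for the zeros

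*SAP*

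**What the plan says.** **The rule.** Rule 3 in SAP section 7.4.1 reads: "If the number of study days in the DB period is less than 70, the month 3 value will not be calculated, but rather imputed". The substitute is the subject's run-in count, so the change is exactly zero. Leavers on days 70 to 83 fall under rule 4, which uses their own diary. A subject whose run-in value is missing gets no zero. The ITT set "includes all randomized subjects with at least one verified treatment post-training during the 12 week randomized period", so treated early leavers stay in the primary t-test.

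**The checks.**
- Section 8.4.1 plans MI and a control-based pattern-mixture model (PMM) for the values imputed under 7.4.1.
- For the MI, Appendix 1 says: "The following factors/covariates will be included in the model: treatment, center and number of migraines in the 4-week run-in period". The PMM has the same list.
- The example code has one post-baseline variable: "var trt center base depvar" for the MCMC step and "var center base depvar" for the PMM.
- Appendix 1 also says that "any non-monotone missing data patterns will be made monotone by imputing the intermittent missing data".
- The two ANCOVAs in 8.4.1 keep the zeros. The complete-population analysis (8.4.3.5) drops imputed subjects. The conditional per-protocol repeat drops early leavers too, since section 5.2 lists "The subject did not reach visit 6" as a major deviation.

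Section 6.3 defines Month 1 (days 1-28) and Month 2 (days 29-56), for optional exploratory use.

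**The sample size.** Section 3.5 requires 133 per arm for a 1-day difference and SD 2.5, then: "With 15% drop-out during the randomized treatment period, a total of 160 subjects per treatment group".

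**The concern.** The checks are there to show whether the zeros drive the result. A subject who leaves between days 57 and 69 can have two full months in the diary, yet every check either keeps the zero, drops the subject, or predicts Month 3 without those months. If leaving depends on early response, that dependence is visible only in the data left out. Appendix 1 speaks of intermittent patterns, which suggests repeated measurements, but with a baseline and one outcome the listed model cannot use the interim months.

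The second issue is smaller. The dropout allowance in section 3.5 fits an analysis without the leavers, whereas the planned analysis keeps those before day 70 as zeros. The section does not say which subjects its planning difference and SD describe.

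**Working it through.** **1. The plan's own figure.** Two-sample t-test, two-sided 5%, 90% power, 1 day, SD 2.5: 133 per arm (power 90.1%), as stated. Dropout: 133/0.85 = 156.5, so 157; the plan's 160 is slightly above. 160 × 0.85 = 136 per arm gives 90.8%. Section 3.5 therefore treats leavers as removed.

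**2. Bias of rule 3.** Let q be the share of an arm scored zero and d those subjects' mean Month 3 change had they stayed. Relative to everyone staying,

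bias (active − sham) = qS·dS − qA·dA; negative favours active.

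It is zero if leavers would not have changed or if the two products are equal.

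**3. Dropout linked to response in active only.** All inputs are assumed:
- run-in and the three monthly counts are normal with equal correlations of 0.5 or 0.7, and SD of change is 2.5;
- 15% of each arm leave before day 70, and half of the leavers lack Month 2;
- sham dropout is random; active leavers' Month 1 change is 1.9 days worse than the arm mean.

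Equal correlations carry about half of that shift to Month 3, about 0.94 day.

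*No true effect, both arms improving 2 days.* dS = −2 and dA = −2 + 0.94 = −1.06. Rule 3: 0.15 × (−2) − 0.15 × (−1.06) = −0.14. Complete population: −0.15 × 0.94/0.85 = −0.17. Simulated differences favouring active:

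| Analysis | False difference (days) |
|---|---|
| Rule 3 | 0.14 |
| Complete population | 0.16-0.17 |
| MI as written | 0.08-0.12 |
| PMM as written | 0.07-0.10 |
| MI with Months 1-2 | about 0.00 |

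Two-sided rejection at correlations 0.5/0.7 (4,000 trials): rule 3 8.2%/8.4%, MI as written 5.3%/7.3%, MI with Months 1-2 4.7%/5.3%. If the link is the same in both arms, none of these analyses is biased.

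*True 1-day effect, sham improving 2 days.* dA = −3 + 0.94 = −2.06. Rule 3: 0.15 × (−2) − 0.15 × (−2.06) = +0.01. Simulated estimates of the true 1.00: rule 3 0.98-0.99, PMM 0.92-0.94, MI as written 1.08-1.11.

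**4. Power with the zeros kept.** Suppose 1 day and SD 2.5 describe completers, with completer mean m and zero share q equal in both arms. The arm mean is (1 − q)m and its variance is (1 − q) × 6.25 + q(1 − q)m².

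Example, q = 0.15, sham −2, active −3: variances 5.3125 + 0.1275 × 4 = 5.82 and 5.3125 + 0.1275 × 9 = 6.46; pooled SD 2.478; difference 0.85; power 86.4%.

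Power at 160 per arm (t-test), by assumed sham improvement:

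| Zero-scored | 0 days | 1 day | 2 days | 3 days |
|---|---|---|---|---|
| 5% | 93.4% | 93.1% | 92.4% | 91.2% |
| 10% | 92.1% | 91.3% | 89.6% | 87.1% |
| 15% | 90.5% | 89.1% | 86.4% | 82.2% |

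If 1 day and SD 2.5 already describe all ITT subjects, power is 94.6%.

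**The case against.** **The plan already has several checks, including one for data missing not at random.** This is the strongest reply, and much of it stands. In the adverse no-effect case above, a simulation without centre (2,000 trials, 20 imputations) has the PMM rejecting in 4.5% and 3.8% of trials at the two correlations. Rule 3, complete population, MI and PMM were all significant in favour of active in 3.5% and 3.1%, against 2.5% for one nominal two-sided test. A reader might infer that agreement among the checks would be broadly misleading. The documents do not support that: it takes response-linked dropout in one arm only and little or no true effect, and even then the excess is about one percentage point.

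**The code is only an example, and Appendix 1 mentions intermittent data.** The wording could be read as allowing earlier assessments. But the text, not just the code, gives a closed covariate list without them. At best the plan is ambiguous.

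**Zero change is conservative.** Not by construction. With no effect, both arms improving 2 days, and 10% of active and 20% of sham scored zero, the bias is 0.20 × (−2) − 0.10 × (−2) = −0.20 day, favouring active. If leavers would have changed as completers did, however, the existing complete-population analysis is unbiased and would show this.

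**15% zeros is too many.** Correct as a limit: rule 4 leavers and subjects with no verified treatment are not scored zero, so 15% is the upper bound under the planned dropout.

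**Conclusion.** The gap is real and small. As written, no check uses the early leavers' Month 1 and Month 2 counts, and adding them to the MI removes a lean of about 0.07 to 0.17 day in one specific adverse case. That size rests on the assumed dropout mechanism, correlations and 15% share. At the planned 1-day effect rule 3 is almost unbiased, with the PMM below and the MI above the truth. This is an improvement to consider, not a flaw that undermines the primary result.

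On power, a reader might infer that the trial is underpowered. The plan does not establish that. Its 133 and 160 are arithmetically sound. The loss appears only if the planning figures describe completers, and it is material only if many are scored zero and sham improves by about 2 days or more. The SAP gives neither quantity. What is missing is the statement of which population 1 day and SD 2.5 describe.

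**What to change.** 1. **Appendix 1, ordinary MI.** Make the covariates treatment, center, run-in count, Month 1 count and Month 2 count (`var trt center base m1 m2 m3`). Add a partial-month rule, for example: scale by 28/x when at least 21 of the 28 days are recorded, matching the run-in rule; otherwise treat the count as missing and impute it in the monotone sequence. A day-45 leaver, with 17 days of Month 2, would have Month 2 imputed.
2. **Appendix 1, PMM.** Keep the present sham-based model unchanged. Putting Months 1-2 into it would make it less severe on active: with a true 1-day effect and 15% random dropout its estimate would rise from 0.85 to 0.91-0.93 day.
3. **Section 3.5.** State whether 1 day and SD 2.5 describe completers or all ITT subjects. If completers, give power at 160 per arm over a range of zero-scored shares: 93.4-91.2% at 5%, 92.1-87.1% at 10% and 90.5-82.2% at 15% (the upper bound), for an assumed sham improvement of 0-3 days. If all ITT subjects, 94.6%.

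The cost is SAP wording and a few lines of code before unblinding, with no new data or subjects. The revised MI still assumes missing at random given run-in and Months 1-2, gains little for those leaving before day 28, and leaves unused the up to 13 Month 3 diary days of subjects leaving on days 57-69. Rule 3 as primary and the sample size need no change.

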4. If number of study days in the DB period is greater than or equal to 70, but less than 84, the month 3 value would be calculated as:

$$\text{Month 3 Value} = \sum_{i=1}^z \text{Day } i, \text{ where Day } i = 1 \text{ (had a migraine)}$$

where  $z$  represents the subject's last day of participation with diary data present.

To ensure consistency of this value for all subjects, the value will be adjusted to reflect an estimated number of days with migraine per 28 day interval. For example, if a subject records data for  $x$  days out of 28 days and have  $y$  days with migraine, then the adjusted number of days with migraine in 28 days is  $(28/x)*y$ , with a maximum value of 28.

Then the change from Run-in is calculated using the adjusted values as:

$$\text{Change}_{\text{Run-in}} = \text{Month 3 value} - \text{Run-In value}$$

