$$\text{Month 6 OL Value} = \sum_{i=141}^{168} \text{Day } i, \text{ where Day } i = 1 \text{ (had a migraine)}$$

In the event that a subject does not have at least 154 days in the OL period the following rules will be used to calculate the Month 6 value:

1. If the number of study days in the OL period is less than 154, the month 6 OL value will not be calculated, but rather imputed to the Month 3 OL value (and thus resulting in a  $\text{Change}_{\text{OL6}} = \text{Change}_{\text{OL3}}$ , implying no change between the 6 month OL and 3 month OL periods).

$$\text{Month 6 OL Value} = \text{Month 3 OL Value}$$

2. If number of study days in the OL period is greater than or equal to 154, but less than 168, the month 6 OL value would be calculated as:

$$\text{Month 6 OL Value} = \sum_{i=1}^z \text{Day } i, \text{ where Day } i = 1 \text{ (had a migraine)}$$

where  $z$  represents the subject's last day of participation (within 168 days) in the OL period with diary data present.

To ensure consistency of this value for all subjects, the value will be adjusted to reflect an estimated number of days with migraine per 28 day interval. For example, if a subject records data for  $x$  days out of 28 days and have  $y$  days with migraine, then the adjusted number of days with migraine in 28 days is  $(28/x)*y$ , with a maximum value of 28.

Then the change from Run-in is calculated using the adjusted values as:

$$\text{Change}_{\text{OL6}} = \text{Month 6 OL value} - \text{Run-In value}$$

Results will be stratified by randomized treatment group.

In addition, the change from the double-blind period to 3 and 6 months of the open label period will be calculated or derived in the same manner for the comparison of the run-in to double-blind, randomized phase. Results will be stratified by randomized treatment group. For the calculation of percent change from the double-blind period to each of the open label periods, if there were zero migraine days at the double-blind period, percent reduction will be imputed as 100%.

$$\text{Change}_{\text{OL3DB}} = \text{Month 3 OL value} - \text{Month 3 value}$$

$$\text{Change}_{\text{OL6DB}} = \text{Month 6 OL value} - \text{Month 3 value}$$

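### For subjects with 70 to 83 study days, the primary Month 3 value is summed from Day 1 instead of Day 57

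*SAP*

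**What the plan says.** All places are in the SAP.

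- Section 7.4.1 defines the primary endpoint as the "change from run-in to the last four weeks (Month 3) of the randomized period in the number of migraine days". Its main formula sums the daily migraine indicator over Days 57 to 84, which is also Month 3 in the table in Section 6.3.
- Rule 3 of that section covers fewer than 70 double-blind study days: "the month 3 value will not be calculated, but rather imputed to the run-in value".
- Rule 4 covers 70 to 83 days. If the number of study days is "greater than or equal to 70, but less than 84, the month 3 value would be calculated as" a sum whose printed limits are Day 1 and z, where z is the last day of participation with diary data. The count is then scaled by (28/x)*y, where x is described as recorded days out of 28 and y as days with migraine, "with a maximum value of 28".
- Section 7.4.2 follows the same pattern for Month 6 of the open-label period. The full formula sums Days 141 to 168. The rule for 154 to 167 days sums from Day 1 to z.
- Table 2 allows Visit 6 at Day 84 plus or minus 5.

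**The concern.** One variable, the Month 3 value, has two incompatible definitions, and which one a subject gets depends on the side of Day 84 on which that subject's data end. Code written from rule 4 as printed would not return a Month 3 value.

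The rule also reaches beyond dropouts. Visit 6 may fall on Days 79 to 89, so a subject who completes on schedule on Days 79 to 83 (five of the eleven permitted days) comes under rule 4.

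Percentage reduction and responder status are built from the same change score. Section 7.4.2 derives headache days and acute-medication days in the same way as the primary endpoint.

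The planned checks catch this only in part:

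- **Multiple imputation and pattern-mixture analyses (Section 8.4.1).** These concern values that Section 7.4.1 imputes. Section 7.4.1 says that rule 3 imputes and rule 4 calculates, so on the plain wording rule 4 values are not replaced.
- **Complete-population analysis (Section 8.4.3.5).** It keeps non-imputed data, so rule 4 values stay in.
- **Per-protocol analysis (Section 5.2).** It is run only if the two populations differ by more than 5%. It removes subjects who did not reach Visit 6 but keeps completers seen on Days 79 to 83.

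**Working it through.** The SAP gives no figure for rule 4 to reproduce. The yardstick is its 1-day design difference (Section 3.5). The 133 per group stated there for SD 2.5 and 90% power is reproduced with the noncentral t distribution, and nothing below depends on it.

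**1. Days outside the target window**, from the printed limits alone.

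- Rule 4, share before Day 57 = 56/z: 56/70 = 80%, 56/79 = 71%, 56/83 = 67%.
- Short Month 6 open-label rule, share before Day 141 = 140/z: 140/154 = 91%, 140/167 = 84%.

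**2. Whether the scaling repairs it.** Let A be the migraine rate per 28 days over Days 1 to 56 and B the rate over Days 57 to z, with complete diaries. If x and y both cover Days 1 to z, then

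rule 4 value = (28/z) × [2A + B(z − 56)/28] = B + (56/z)(A − B).

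So each value is off by (56/z)(A − B). With an assumed 8, 6 and 4 migraine days in Months 1, 2 and 3 (A = 7, B = 4), rule 4 gives 6.4 at z = 70 and 6.0 at z = 83. Summing from Day 57 gives 4.0 in both cases.

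If instead y is the printed sum and x counts only Days 57 to z, the windows do not match. At a constant 8 per 28 days and z = 70, y = 8 × 70/28 = 20 and x = 14, so (28/14) × 20 = 40, capped at 28.

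**3. Treatment difference among rule 4 subjects**, matched x and y. Assume a Month 3 effect of 1 day and let f be the Months 1–2 effect divided by the Month 3 effect. Effect shown = 1 − (56/z)(1 − f). At z = 81, 56/81 = 0.691:

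| f | effect shown (days) |
|---|---|
| 0 | 0.31 |
| 0.5 | 0.65 |
| 1 | 1.00 |
| 1.5 | 1.35 |

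**4. Overall treatment difference** = 1 − s(56/z)(1 − f), where s is the share of subjects under rule 4, taken as equal in both arms. The SAP does not give s. Over z = 70 to 83 and f = 0 to 1.5, the extremes occur at z = 70:

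| assumed s | f = 0 | f = 1.5 |
|---|---|---|
| 5% | 1 − 0.05 × 0.8 = 0.96 | 1 + 0.05 × 0.8 × 0.5 = 1.02 |
| 10% | 0.92 | 1.04 |
| 15% | 0.88 | 1.06 |

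The 15% equals the whole drop-out assumed in Section 3.5, so it is an upper limit for dropouts alone. Completers on Days 79 to 83 come on top.

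**5. Responder status.** Assumed subject: run-in 8, then 7, 6 and 3 migraine days in Days 1–28, 29–56 and 57–81.

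- Rule 4: 28 × 16/81 = 5.53; reduction 1 − 5.53/8 = 31%, non-responder.
- Days 57–81: 28 × 3/25 = 3.36; reduction 58%, responder.
- With 4 instead of 3 days in the last interval: 5.88 (27%) against 4.48 (44%), so the status does not change.

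**The case against.** The best defence is that the intent can be recovered. The cut-offs 70 and 154 each leave exactly 14 days of the target window (70 − 56 and 154 − 140). The scaling text speaks of days out of 28, and the section opens with the last four weeks. A careful programmer might correct the limit unprompted. This stands as evidence of what was meant and supports the correction proposed here. It does not rescue the printed formula, which gives a different number if followed.

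Further points:

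- **Mismatched x and y.** This is a strained reading, because the scaling sentence most naturally counts y on the same x days. Accepted: the figure of 40 is a worst case and the conclusion does not rest on it.
- **Size.** At a 5% share and these values of f, the overall difference moves by at most 0.04 day. Also true, but the shares are assumptions and do not bound the number of early-visit completers.
- **Constant effect.** A treatment effect constant over time removes the bias only if the rule 4 share and z are similar in both arms. Otherwise it need not: with assumed shares of 10% and 5%, z = 81, and a Months 1–2 rate 2 days above Month 3 in both arms, the bias is 0.05 × (56/81) × 2 = 0.07 day.
- **Day numbering.** Table 2 puts Visit 2 at Day 1, while Section 6.1 puts randomization at Day 0 and subtracts a further day from the week 12 assessment onward. The edge of the affected group is therefore uncertain by about a day.
- **Month 6 open-label.** This is a secondary outcome with both groups on the active device, so it cannot alter the randomized comparison. It is the lesser part of the point.

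**Conclusion.** The concern holds. Rule 4 contradicts the SAP's own definition of the primary endpoint, nothing else in the document repairs it, and it must be corrected before unblinding.

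What is certain, from the limits alone, is that 67% to 80% of the days entering a rule 4 value lie outside Month 3, and 84% to 91% of those entering a short Month 6 open-label value lie outside Month 6. The size and direction of any bias in the treatment difference depend on the time course of the effect and on the number of subjects under the rule, neither of which the SAP gives. The range of 0.88 to 1.06 day is an illustration under assumed shares up to 15%, equal in both arms, with complete diaries and matched x and y; it is not a bound. The severity rests on the primary endpoint having two definitions, more than on that range.

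**What to change.** **Needed**

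- Rule 4: sum from Day 57 to z. Let x be the diary days recorded in Days 57 to z and y the migraine days on those same days, then apply (28/x)*y.
- Short Month 6 open-label rule: sum from Day 141 to z in the same way.

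**To settle in the same revision**

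- State a minimum x below which the value is treated as missing and handled as under rule 3 or its open-label counterpart. A minimum of 21, as used for the run-in, cannot be met before z = 77 (Days 57 to 77 are 21 days). It would in effect move the cut-off from 70 to 77, so state a lower minimum if that is not wanted.
- State whether the Visit 6 day counts as a double-blind day. Section 6.1 makes it open-label day 0. On a count from Day 1 that excludes it, a visit exactly on Day 84 leaves 83 days and falls under rule 4.
- Query: both Month 3 open-label sums in Section 7.4.2 start at Day 1, while Section 6.4 puts that month at Days 57 to 84. The surrounding text also speaks of 3-month periods, so a 12-week average may be intended. State which and, if 84 days, define x so that the result is on a 28-day scale.
- Minor: the run-in limits −z−28 to −z contain 29 terms; write the sum with 28, as Section 6.2 describes.

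**Alternative.** A window of the last 28 observed days is acceptable if stated before unblinding. It has less scaling noise, but with complete diaries 14/28 = 50% (z = 70), 5/28 = 18% (z = 79) or 1/28 = 4% (z = 83) of its days lie before Month 3.

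**Cost.** SAP wording and derivation code only; no new data. The price is noisier values for subjects scaled up from 14 to 27 days.
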